# Intervention

This research protocol focuses on one type of regulatory intervention that local authorities have discretion to implement or not implement. The Housing Act 2004, and subsequent revisions in 2015, gave local authorities discretionary powers to implement **selective licensing (SL)** schemes [5]. SL requires landlords in geographically defined areas to pay for a 5-year licence. Fees vary but are around £600 [9,10]. The fees help finance the local authority's regulation of PRS in that area (e.g. housing inspections) although they may not cover the full costs to local authorities. When local authorities inspect PRS homes and find them to be substandard, landlords are expected to pay for the improvements necessary to meet the legal standards.

SL applies to privately rented properties occupied by a single household. Nine out of ten PRS homes meet this description. Houses that include multiple households (Houses in Multiple Occupation or HMOs) are not covered by SL. HMOs have separate license schemes not covered by this study.

Local authorities must obtain approval from national government if a proposed SL scheme covers >20% of their geographical area or affects >20% of privately rented homes in the local authority area. In this study, we will call these 'larger' SL schemes. SL schemes covering up to 20% can be implemented by local authorities without applying for this national government approval. We will call these 'smaller' SL schemes. The smaller schemes therefore have a simpler approval mechanism and they occur most frequently as zoned sub-areas within local authority boundaries.

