Furthermore, we hypothesise a number of barriers in our proposed pathways to impact (See logic model). For example:

9. NON-COMPLIANCE HYPOTHESIS. Intervention effects may be reduced due to landlord non-compliance at any stage on the pathway to impact (e.g. applying and paying for licenses,

- meeting conditions of licenses, co-operating with the inspection regime, and refurbishing sub-standard properties).
- 10. PARTIAL IMPLEMENTATION HYPOTHESIS. Implementers may lack resource (e.g. finance, workforce) or face other barriers that prevent full implementation.
- 11. LOCAL VARIATION HYPOTHESIS. Local variation in the implementation of SL may lead to local variation in impacts. Local variation can at times be considered positively (e.g. tailoring to local needs) or negatively (e.g. inequities / 'post-code lottery').

WP1 and WP3 include quantitative analyses to identify potentially detrimental effects and (in)equity, while WP2 will use qualitative methods to explore unintended consequences, as well as barriers and facilitators to planned/desired impacts.

We note that we have found it difficult to represent all of these hypotheses diagrammatically in the logic model – we found a mixture of text (ie. above) and diagram easier to work with.

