		7) The sample has changed slightly for two reasons, a) we now restrict the analyses to schemes implemented 2012-2019 as the SDID method requires at least 1 pre-intervention time period. Before the sample included three small schemes implemented in 2011: 2011_NewcastleuponTyne, 2011_Stoke-on-Trent, and 2011_Thanet (Section 18. Analysis Plan), b) the SL scheme data have been revised following a data validation consultation (25 Sep-8 Nov 2024): Sheffield 2014 has been recorded as a street-based scheme (N=2 LSOA) and newly treated areas of 2020_Wirral has been recoded as a 'Future treated scheme 2020-21' (N=2 LSOA).
		8) In consultation with ISC, we have dropped or simplified some of the secondary subgroup analyses due to multiple testing concerns. False Discovery Rate corrections will furthermore be applied to secondary analyses (Section 18. Analysis Plan).
		9) In consultation with DMEC, we have updated the Conflict of Interest statement to reflect that some members reside in local authorities that have or had Selective Licensing schemes.

3. Summary

Scientific abstract (WP1, 3)

Research question

Can selective licensing (SL) schemes improve England's private rented housing sector leading to health and social benefits for residents?

Background

English local authorities can implement SL to help improve conditions and reduce antisocial behaviour (ASB) linked to private rented housing. SL requires private rented landlords to register, purchase a license with various conditions, and allow inspections to ensure housing standards are maintained. A London study of SL found evidence of impacts but a national study is needed.

Study Aim

To evaluate SL schemes for the private rented housing sector in England. The evaluation will assess health and social impacts, implementation and change mechanisms, and economic consequences.

Work package objectives

WP1: To assess individual-level and area-level impacts of SL schemes on health and social outcomes. To assess impacts on equity.

WP3: To assess whether SL schemes are value for money.

Methods

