 - Area level: mental health and wellbeing (SAMHI: primary outcome); physical health (operationalised as all-cause emergency hospital admissions, cardiovascular emergency admission in 65+yr, respiratory emergency admission in 65+yr, emergency admission injuries falls/burns in 65+yr (any place of occurrence), asthma emergency admission (all ages, 65+yr), all-cause A&E attendance (all ages, 0-14yr, 65+yr)); ASB, population turnover, £ rent.
 - Individual level: self-reported anxiety (primary outcome); general self-reported health, residential stability (ONS Annual Population Survey APS).

8c. Purpose

The impact assessment intends to estimate causal effects.

Part C: METHODS

9. Design and setting of study

9a. Study design

WP1 Impact evaluation: Individual-level outcomes

The impact evaluation has a difference-in-differences design with matched controls. The idea of a difference-in-differences design is to supplement a simple before-after comparison of the outcomes of interest in the treated units with a before-after comparison of the outcomes in a set of control units to remove any changes that would have happened in the absence of the intervention. The underlying assumptions is that in the absence of the intervention the average before-after change would have been the same in the treated units and in the control units, known as the parallel trends assumption.

When considering individual-level outcomes, treated units are private rented sector tenants in LSOAs with SL. Potential control units are individuals who do not live in private rented sector housing or who do not live in LSOA with SL. However, SL might have spillover effects. For example, many SL schemes are set up to tackle anti-social behaviour. If they were effective at addressing anti-social behaviour, individuals in SL areas who do not live in private rented housing might also benefit from SL. Using these individuals as controls might therefore result in underestimating the impact of SL. Similarly, individuals in neighbouring LSOAs who do not have an SL scheme in place might be affected by the SL scheme if, for example, SL leads to displacement of certain types of private sector tenants such as tenants engaged in anti-social behaviour. Using these individuals as controls might result in overestimating the impact of SL.

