WP3 Cost-benefit analysis using subjective wellbeing approach

The economic evaluation will produce a cost-benefit analysis that uses the subjective wellbeing approach to monetise the benefits of SL. The starting point for the calculation of the benefits of SL will be the estimate of the impact of SL on the life satisfaction variable from the APS, one of our individual-level outcome measures. We will then follow the procedure described in Dolan et al. (2019) [11]. Essentially, we will use an estimate of the impact of income on life satisfaction from previous research to determine the income change that would be required to achieve the same change in life satisfaction as achieved by SL. Multiplying this income change amount by the number of individuals affected by SL will provide the total benefit of SL from a societal perspectives. All our calculations will be retrospective and estimate the benefits of SL over our 2012 to 2019 sample period. Depending on the results of our analysis of spillover effects, we will adjust the benefit estimate accordingly.

We will calculate the costs of SL from a public sector perspective and attempt to estimate the costs of SL from a societal perspective. To determine the total cost of SL from a public sector perspective over the 2012 to 2019 sample period, we will measure the direct and indirect cost of SL in four case study sites. Accounting data provided by the case study sites will be the starting point for the cost calculation. However, the economic concept of opportunity cost goes beyond accounting cost. For example, local authorities might employ staff specifically for the administration of the SL schemes in their area, so these costs would be included in the accounting data as staff salaries and on-costs. However, staff not specifically employed for SL purposes might also be involved in administering local schemes. Any staff involved in SL will require office space and might need to be trained and supervised. Local authorities need to disseminate information about their SL schemes using their website or other means and maintain the online application system. All these activities incur costs, either directly in the form of money being handed over in payment or indirectly in the form of resources such as staff time or office space not being available for alternative uses.

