The four case study sites have been selected to represent different types of SL (smaller and larger) in different regional contexts (north and south). We will use extrapolation methods that use these two broad characteristics as well as cost information obtained through FOI requests to assign costs to the other local authorities that have implemented SL. We will subtract income from license fees, fines and civil penalties to obtain net costs.

In addition, we will estimate the potential costs saved by the NHS through SL's impact on antidepressant prescribing, mental-health related hospital admissions and all-cause hospital admissions over our sample period. If possible, we will also estimate potential cost savings through impacts on mental health-related benefits. If we find substantial cost savings, we will subtract these from the cost of SL to local authorities to obtain net costs from a public sector perspective.

To estimate net costs from a societal perspective we will add back in any income local authorities generate from license fees, fines and civil penalties and try to estimate the costs landlords incur to remove hazards following the receipt of an improvement notice issued by the local authority following an SL inspection.

9b. Study setting

WP1 and WP3 will examine impacts across England.

10. Study schedule

Start date: 1st December 2023

Length: 26 months.

- 0-3 months: ethics approval, PPI & AG meetings
- 2-6 months: WP1 update data, submit protocol
- 7-17 months: WP1 Analysis plan and analysis; WP3 prepare data
- 18-22 months: All WPs: Analysis, interpretive workshops; refine and begin write-up
- 22-26 months: final analysis and write-up.

11. Sample size

Individual-level outcomes

For the individual-level outcome measures, we estimate that the APS includes about 1,000 respondents per year who live in private rented accommodation in LSOAs covered by SL schemes, so over our 2012 to 2019 sample period we expect to observe around 8,000 individuals in the intervention group (5.5% of the England population live in the schemes included in the study). The number of APS participants in the matched comparison LSOAs will be approximately 3000 per year if we match 3 control LSOAs to every intervention LSOA.

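### The societal cost counts landlords' works only after a formal improvement notice, while the benefit is the whole effect of licensing, so works done without a notice enter the benefit but not the cost.

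*SAP*

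**What the plan says.** Section 9a of the SAP, under the WP3 cost-benefit heading, starts from a public-sector net cost and moves to a societal cost in two steps. It will "add back in any income local authorities generate from license fees, fines and civil penalties", and it will "try to estimate the costs landlords incur to remove hazards following the receipt of an improvement notice issued by the local authority", the notice being one that follows a licensing inspection. Section 9a of the Protocol has the same text. No other landlord cost is named in either place.

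The benefit starts from "the estimate of the impact of SL on the life satisfaction variable from the APS". It is then scaled up: "Multiplying this income change amount by the number of individuals affected by SL will provide the total benefit of SL from a societal perspectives". An adjustment for spillover may follow. The effect rests on area exposure, since "treated units are private rented sector tenants in LSOAs with SL".

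The documents describe a mechanism wider than notices. Protocol 7a (Intervention) says that when an inspection finds a home substandard, "landlords are expected to pay for the improvements necessary to meet the legal standards". The SAP summary says landlords must "purchase a license with various conditions, and allow inspections to ensure housing standards are maintained". Hypothesis 9 in Protocol 7c lists, among the steps on the pathway to impact, "meeting conditions of licenses, co-operating with the inspection regime, and refurbishing sub-standard properties". None of these passages makes the landlord's outlay depend on a formal notice.

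**The concern.** A cost-benefit comparison needs the same set of induced changes on both sides. Here the benefit takes in every route by which licensing may improve tenants' lives. The landlord side of the cost takes in one route only, hazard removal after a notice. Works done to meet licence conditions, in anticipation of an inspection, or at an inspector's request without a notice would be left out, as would the landlord's time spent on compliance.

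The contrast with the local authority side is marked. There section 9a insists on opportunity cost beyond the accounts, down to office space, training and supervision. Neither document justifies the notice-only limit, lists it as a limitation or plans a sensitivity analysis for it.

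WP3 asks whether licensing is value for money, and Protocol section 21 names a benefit-cost ratio as its outcome. If that ratio, or a second one, is reported from a societal perspective, the omission bears directly on it.

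**Working it through.** The documents give no cost, benefit or ratio, so there is no figure to reproduce. The check compares the scope of the two sides and then shows how the gap would act on a ratio.

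**Scope, side by side**

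| Licensing-induced change | In the benefit? | In the societal cost? |
|---|---|---|
| Hazard removal after an improvement notice | Yes | Yes, if it can be estimated |
| Improvement after inspection without a notice | Yes | No |
| Works to meet licence conditions or before inspection | Yes | No |
| Landlord compliance and management time | Any resulting effect, yes | No |

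**Direction and form.** Let C be the societal cost other than landlord works (local authority cost after income is added back, less any NHS saving the plan deducts), set to 1. Let R be all landlord works induced by licensing, as a multiple of C. Let s be the share of those works that follows a notice.

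- Planned cost: 1 + sR
- Full cost: 1 + R
- The benefit is the same in both, so planned ratio / full-cost ratio = (1 + R) / (1 + sR)

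This exceeds 1 whenever R > 0 and s < 1. Neither R nor s is in the documents; the values below are assumptions.

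| R | s = 0.10 | s = 0.25 | s = 0.50 | s = 0.75 | s = 1 |
|---|---|---|---|---|---|
| 0.25 | 1.22 | 1.18 | 1.11 | 1.05 | 1.00 |
| 1 | 1.82 | 1.60 | 1.33 | 1.14 | 1.00 |
| 5 | 4.00 | 2.67 | 1.71 | 1.26 | 1.00 |

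For example, R = 1 and s = 0.25 give 2 / 1.25 = 1.60.

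**Rent pass-through.** Suppose a share p of the uncounted works is recovered through rent and already lowers tenants' life satisfaction. Only the rest is missing from the comparison, and the factor becomes [1 + sR + (1 − p)(1 − s)R] / (1 + sR). With R = 1 and s = 0.25:

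- p = 0: (1.25 + 0.75) / 1.25 = 1.60
- p = 0.5: (1.25 + 0.375) / 1.25 = 1.30
- p = 1: 1.25 / 1.25 = 1.00

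**If the attempt fails.** The plan only promises to try. If the notice-related cost cannot be obtained, the planned cost is 1 and, before pass-through, the factor is 1 + R, or 2.00 at R = 1.

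**The case against.** The strongest reply is that the direction holds only with everything else fixed.

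- **Pass-through.** Hypothesis 4 in Protocol 7c expects landlords may raise rents to cover refurbishment and fees. To that extent the cost already sits in the measured benefit, and adding all works would count it twice. This stands as a limit. It does not explain the notice-only rule, because the plan adds fees back and counts notice-related works without netting any pass-through.
- **Other imbalances.** Benefits are counted only to 2019, although Table S1 shows many schemes starting in 2018 or 2019, and this could work against licensing. The benefit also contains no gain to owners, though hypotheses 2 and 3 expect higher property values. Both points stand.
- **Gross or net works.** The benefit is measured against matched controls. A count of all works would include repairs that landlords would have made anyway and could overstate cost. This stands and shapes the fix.
- **How much work happens without a notice?** The documents do not say, and the conditions that Protocol 7c describes from the London study concern anti-social behaviour rather than repairs. This limits any statement of size but does not remove the mismatch in definition.
- **Reach.** The public-sector costing is the firm commitment and the societal one is tentative. That is true, and the point concerns the societal result only.

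A reader might go further and infer that the whole comparison is tilted towards licensing, or that the omission can be priced. The documents support neither. The offsetting items above are unquantified, and a price would need dwellings affected, unit repair costs and the notice share, none of which is given.

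**Conclusion.** The point holds as a mismatch of scope. As written, the societal cost understates licensing-induced landlord cost whenever any such work happens without a notice. Taken alone and before pass-through, that raises the societal benefit-cost ratio.

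The factor of 1.05 to 4.00 is illustrative. It rests on assumed landlord works of 0.25 to 5 times the other societal cost and an assumed notice share of 0.10 to 0.75. It is 1.00 if every induced repair follows a notice, or if the omitted cost is fully passed on and already in the benefit. The net bias of the whole ratio is not established, and the public-sector result is unaffected.

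A related gap makes the consequence harder to read. Protocol section 21 does not say which cost perspective the benefit-cost ratio uses, and the WP3 text in Protocol section 18 costs licensing from the public-sector perspective only, whereas section 9a of both documents adds a societal one.

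**What to change.** - Define landlord cost as all works and compliance costs induced by licensing, with or without a notice, net of repairs expected without licensing.
- Use the compliance and enforcement data that WP2 will collect from the four case-study sites (Protocol section 18, document analysis) wherever they record such work. Nothing in the plan shows that they capture works without a notice or their cost, so some inputs may have to be assumed or sought separately.
- Report the societal ratio over a low-high range of unit cost, share of works following a notice, and rent pass-through, the last to avoid double counting. Show the notice-only figure as the lower bound on cost, on the same net-of-expected-repairs basis.
- State which cost perspective the ratio in Protocol section 21 uses, and reconcile the WP3 text in Protocol section 18 with section 9a of the Protocol and SAP.

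The price is revised WP3 wording and a scenario table. The societal result becomes a range that rests partly on assumed inputs, and it will probably be less favourable to licensing than the notice-only figure.

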### Area-level outcomes

For the area-level outcomes, our main analysis will examine 1,635 treated LSOAs, which would give a minimum detectable difference of 25% of an SD (Table 1).

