When considering area-level outcomes, treated units are LSOAs with SL. Potential control units are LSOAs without LSOA. However, SL might have spillover effects. Neighbouring LSOAs who do not have an SL scheme in place might be affected by the SL scheme if, for example, SL leads to displacement of certain types of private sector tenants such as tenants engaged in anti-social behaviour. Using these LSOAs as controls might result in overestimating the impact of SL. We therefore use as our potential controls LSOAs without SL that are not direct neighbours of LSOAs with SL. From among these potential controls, we choose LSOAs that we have matched to the treated LSOAs using characteristics of the LSOAs such as proportion of individuals who are under 16, proportion of individuals who are non-white and proportion of households classed as overcrowded.

The starting point for our analysis of the area-level outcomes is the following two-way fixed effects regression specification:

$$Y_{at} = \alpha_a + \varphi_t + \beta D_{at} + \varepsilon_{at}$$

 Y_{at} indicates one of our outcome measures for LSOA *a* in year *t*. α_a is an LSOA effect, which accounts for time-invariant differences between the LSOAs, and φ_t is a year effect, which accounts for changes over time happening in all LSOAs. D_{at} takes the value 1 if LSOA *a* is subject to an SL scheme in year *t* and 0 otherwise. β is the treatment effect, i.e. it captures the impact of the SL scheme. Because of the staggered intervention timing we will apply the Callaway and Sant'Anna estimator and estimate all relevant group-time average treatment effects and then summarise them using different aggregation schemes [6].

As for the individual-level outcomes, we will assess the plausibility of the parallel trends assumption by examining the trends in the outcome measures for the treatment and control units in the before period by plotting the raw data and by running an event study regression for each group. In case the parallel trends assumption is implausible, we will use Synthetic Difference-in-Differences (SDID) instead of DiD as the primary method [8,9].

SAP Version 1.0

p.10

We will explore spillover effects by repeating the difference-in-differences analysis with matching for LSOAs that are first-order neighbours of SL areas by treating the first-order neighbours of treated LSOAs as if they are intervention LSOAs and matching them to comparable LSOAs that are neither SL areas nor SL area neighbours.

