As the power calculation for our staggered treatment timing difference-in-differences design with repeated cross-section data would be very complicated, we ran a power calculation for the canonical difference-in-difference design with one pre- and one post-intervention observation to get a broad idea of the statistical power of our analysis. The power calculations are based on a bootstrapping algorithm with 1,000 repetitions with 95% significance level and a 3:1 ratio between control to intervention units. The outcome variable was designed as normal-distributed and z-standardised in an artificial dataset. With just 1,000 respondents – the potential annual number of respondents in treated areas – the minimum detectable difference would be 30% of an SD (Table 1).

Table 1 Power calculations based on bootstrapping algorithm with 1,000 repetitions for a DiD design with 95% significance level, one pre- and one post-intervention observation, and 3:1 ratio between control to intervention units (Burlig et al. 2020) [12]. The outcome variable was designed as normal-distributed and z-standardised. Cells shaded in grey indicate power calculations at or above 80%. A unit can correspond to either a respondent or a LSOA area depending on the context. N corresponds to the number of treated units.

Ν	10%SD	15%SD	20%SD	25%SD	30%SD
1000	0.167	0.291	0.523	0.694	0.837
1500	0.195	0.440	0.637	0.864	0.953
2000	0.272	0.540	0.800	0.934	0.989
2500	0.333	0.659	0.884	0.972	0.997
3000	0.379	0.706	0.923	0.987	0.998
3500	0.423	0.787	0.958	0.989	1.000
4000	0.515	0.833	0.979	0.997	1.000
4500	0.568	0.876	0.988	0.999	1.000
5000	0.593	0.894	0.993	0.998	1.000
5500	0.652	0.930	0.993	1.000	1.000
6000	0.685	0.946	1.000	1.000	1.000
6500	0.727	0.962	0.998	1.000	1.000
7000	0.767	0.973	1.000	1.000	1.000
7500	0.755	0.982	1.000	1.000	1.000

p.12

8000	0.797	0.986	1.000	1.000	1.000
8500	0.811	0.992	1.000	1.000	1.000
9000	0.839	0.994	1.000	1.000	1.000
9500	0.850	0.994	1.000	1.000	1.000
10000	0.870	0.999	1.000	1.000	1.000

Area-level outcomes

For the area-level outcomes, our main analysis will examine 1,635 treated LSOAs, which would give a minimum detectable difference of 25% of an SD (Table 1).

12. Sampling procedure

Our intervention group will include all selective licensing schemes in England with start dates between 2012 and 2019, as identified by Freedom of Information (FOI) requests to all English local authorities. Comparison areas will be identified through matching (see Section 18).

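### The area-level detectable difference of 25% of an SD is not the figure for 1,635 treated LSOAs: Table 1 reproduces only with N as total units and uncorrelated before and after values

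*SAP*

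**What the plan says.** Section 11 of both documents gives one power table for two kinds of data. The SAP describes a "bootstrapping algorithm with 1,000 repetitions with 95% significance level and a 3:1 ratio between control to intervention units", and the Table 1 caption a "DiD design with 95% significance level, one pre- and one post-intervention observation". On the simulated outcome it says only: "The outcome variable was designed as normal-distributed and z-standardised in an artificial dataset". No correlation between a unit's before and after values is given. The caption defines N as the number of treated units and adds: "A unit can correspond to either a respondent or a LSOA area depending on the context". The power threshold is 80%, marked by shading.

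Two figures are read from the table. For survey (APS) respondents, 1,000 treated gives 30% of an SD. For areas, the SAP says "our main analysis will examine 1,635 treated LSOAs, which would give a minimum detectable difference of 25% of an SD"; the protocol has the same sentence ("which would give a minimum detectable difference of 25% of an SD").

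The data structures differ. Section 9a says that APS respondents are different people each year. For areas, the model contains a term that "is an LSOA effect, which accounts for time-invariant differences between the LSOAs", and Section 14a says that SAMHI, the area-level primary outcome, is available annually for LSOAs. Controls are matched 1:3 with replacement (Section 18).

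The treated count is itself unsettled. The Section 18 text makes LSOAs with 100% coverage the main analysis (1,356 in Table 2), while the Table 2 caption and Section 11 use the 5%-100% group (1,635).

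**The concern.** Two things do not fit. First, 25% looks too large for 1,635 treated LSOAs with three controls each, even with no gain from repeated measurement. Second, a table that suits fresh respondents each year is applied to a panel of the same LSOAs. There the LSOA effect removes stable differences, and the before-after correlation governs the precision.

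This is the only sensitivity figure given for the area-level primary outcome. Anyone interpreting a small or null SAMHI effect would turn to it. The same table also supplies the figure for the individual-level primary outcome.

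**Working it through.** **Inputs.** Alpha 0.05, taken as two-sided because sidedness is not stated (one-sided fits Table 1 worse); 80% power; 3:1 controls; SD 1; one observation before and one after (all Section 11 and Table 1). The before-after correlation rho is not in the documents.

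**Formula.** For a two-period difference-in-differences with nT treated and nC control units:

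- SE = sqrt(2(1 - rho)(1/nT + 1/nC))
- power = Phi(d/SE - 1.960)
- minimum detectable difference (MDD) = (1.960 + 0.842) x SE

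**Step 1: the table as labelled** (nT = N, nC = 3N, rho = 0).

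- N = 1,500, d = 0.25: SE = sqrt(2(1/1500 + 1/4500)) = 0.0422, so power is 1.000. Table 1 prints 0.864.
- N = 1,000, d = 0.10: power is 0.491. Table 1 prints 0.167.

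The labelled reading does not reproduce. Fitting it would need rho of about -2.9, which is impossible.

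**Step 2: N as total units** (nT = N/4, nC = 3N/4, rho = 0).

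- N = 1,500, d = 0.25: SE = sqrt(2(1/375 + 1/1125)) = 0.0843, so power is 0.842 (printed 0.864).
- N = 1,000, d = 0.30: SE = sqrt(2(1/250 + 1/750)) = 0.1033, so power is 0.828 (printed 0.837).

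Over all 95 cells, 84 agree within 2 percentage points and the largest gap is 4.1. The simulation error with 1,000 repetitions is up to sqrt(0.25/1000) = 1.6 points. The best-fitting rho is 0.03; rho = 0.2 already misses by up to 11.8 points.

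**Step 3: where the 25% comes from.** With 1,635 as total units (408.75 treated, 1,226.25 control), power is 0.697 at 20% and 0.872 at 25%, and the MDD is 22.6%. The printed 25% is therefore the first table column above 80% power on the total-units reading.

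**Step 4: N corrected, rho still 0.**

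- 1,635 treated, 4,905 controls: 2.802 x sqrt(2(1/1635 + 1/4905)) = 11.3% of an SD.
- 1,356 treated, 4,068 controls: 12.4%.
- APS, 1,000 treated and 3,000 controls per period: 2.802 x sqrt(2(1/1000 + 1/3000)) = 14.5%, against the stated 30%.

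**Step 5: the panel.** If SD means the outcome SD, multiply by sqrt(1 - rho). The rho values are assumptions.

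| rho | MDD, 1,635 treated |
|---|---|
| 0 | 11.3% |
| 0.5 | 8.0% |
| 0.8 | 5.1% |
| 0.9 | 3.6% |
| 0.95 | 2.5% |

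**Step 6: what works the other way.**

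- *Clustering.* The 1,635 LSOAs lie in 41 authorities, about 40 each if equal. The design effect is 1 + (1635/41 - 1) x ICC, where ICC is the assumed intra-authority correlation of the change. For ICC 0.01 to 0.20 it runs from 1.39 to 8.78. Multiplying the MDD by its square root gives 13.3% to 33.5% at rho 0, and 6.0% to 15.0% at rho 0.8. Table S1 shows very unequal scheme sizes, so equal clusters is a simplification.
- *Reuse of controls.* The 4,905 matched control places (1,410 + 705 + 2,790, Table 4) are filled by 2,819 distinct LSOAs (Table 3). With equal weights, 1,635 against 2,819 gives 12.3% at rho 0.

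**The case against.** The strongest defence is that Section 11 never says which SD it means. If SD is the within-LSOA residual SD, independent draws are a valid two-period model, because the LSOA effect cancels in the difference. That stands: the documents show an undefined SD and an unstated correlation, not a proven wrong variance. It does not rescue the 25%, because independent draws with 1,635 treated LSOAs give 11.3%.

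Second, the plan offers its two-period calculation only as a rough guide, and the sample is every identified scheme starting in 2012-2019, so no sampling decision hangs on the figure. That limits the importance. But the caveat is attached to the staggered, repeated cross-section design, and the area-level sentence states its figure without qualification.

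Third, sqrt(1 - rho) is a two-period factor, whereas the planned Callaway and Sant'Anna estimator combines group-time effects at several lags. That is fair, and it is why a simulation is preferable to a single correction factor.

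**Conclusion.** The stated 25% of an SD is wrong as written for 1,635 treated LSOAs. Most of the gap comes from N: the table behaves as if N were total units. On its own label the two-period figure with uncorrelated values is 11.3% (12.4% for 1,356). The same error makes the APS figure 14.5% rather than 30% at 1,000 treated respondents. The panel structure lowers the area-level figure further on the outcome-SD scale, to 8.0%-2.5% for assumed rho of 0.5-0.95, before clustering and reuse of controls.

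Three stronger readings are tempting but not supported:

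- That ignoring the panel correlation is what produces 25%. It is not, so scaling the printed 25% by sqrt(1 - rho) carries the N error forward.
- That the study is more sensitive than stated overall. Steps 5 and 6 together span 6.0% to 33.5% for rho 0-0.8 and ICC 0.01-0.20, on both sides of 25%. The documents give neither quantity, so the net direction is unknown.
- That a null SAMHI result will be dismissed as underpowered. Nothing in the documents says results will be judged against this figure.

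The conclusion about N rests on refitting Table 1 with a two-sided test; the panel figures rest on assumed rho.

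**What to change.** In Section 11 of both documents:

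1. Correct N in Table 1, by relabelling it as total units or by re-running it with N treated. Re-read both the area-level and the APS figures. Table 1 should not be kept unchanged for the APS outcomes.
2. Say which SD is meant for SAMHI (outcome or within-LSOA) and give its size in SAMHI units.
3. Restate the SAMHI detectable difference, preferably from a placebo-date simulation on the annual series of never-treated LSOAs. It should keep each LSOA's serial correlation and the grouping by authority, apply the planned estimator, and reflect reuse of controls. At minimum, give a stated rho estimated from those LSOAs together with a clustering allowance.
4. Use the treated count of the main analysis, once the Section 18 text (1,356) and the Table 2 caption and Section 11 (1,635) are reconciled.

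The cost is a short simulation and a few changed sentences, with no change to the sample. No treated-area outcomes are needed. Because the SAP says it precedes any outcome analysis, the use of never-treated SAMHI data should be recorded in the revision log.
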